4. RESEARCH DESIGN AND METHODS

4.A. Overview

The overall hypothesis is that therapy with corticosteroids following portoenterostomy will improve bile drainage and long-term outcome in infants with biliary atresia. This hypothesis will be tested by a multicenter prospective, randomized, double-blinded, placebo-controlled trial. Subjects will be recruited from subjects enrolled in the ChiLDREN prospective observational database study who undergo portoenterostomy for biliary atresia. The investigator or clinical research coordinator will approach the subject's parent(s) or guardian(s) and discuss the study design, benefits and possible risks with the family. After IRB-approved written consent is obtained from the parent or guardian, the clinical research coordinator will:

- Complete the Eligibility Form
- Randomize the subject to 13 weeks of treatment with placebo or corticosteroids. (The research team will be blinded to the treatment. The randomization scheme will be prepared by the DCC and implemented by the research pharmacist.)
- Collect clinical and biochemical data at 2 weeks after portoenterostomy, at 1, 2, 3, and 6 months after portoenterostomy, and at 12, 18, and 24 months of age.

All subjects will receive standard clinical care that is routinely used for all infants with biliary atresia, which will include nutritional support and medications unrelated to this trial. This routine clinical care will not be modified due to participation in this study.

4.B. Study Population

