- Infants with other severe concurrent illnesses such as neurological, cardiovascular, pulmonary, metabolic, endocrine, and renal disorders that would interfere with the conduct and results of the study
- Any other clinical condition that is a contraindication to the use of corticosteroid (e.g., bowel perforation)
- Infants who have received the live attenuated rotavirus vaccine (e.g. Rotateq) within 5 days prior to proposed administration of study drug.

In the unlikely event that the diagnosis of biliary atresia is established during exploratory laparotomy, but the surgeon did not perform a portoenterostomy (as may occur in cases of advanced cirrhosis), the subject will not be eligible for this study.

4.E. Primary and Secondary Outcome Measures

- Primary outcome measure:
Percentage of subjects with serum total bilirubin $<$ 1.5 mg/dL and with native liver at 6 months after portoenterostomy.
- Secondary outcome measures:
All measurements will be made at 12 and 24 months of age (unless noted otherwise):
 1. Serum total bilirubin concentration (and also at 3 months after portoenterostomy)
 2. Survival with native liver at 24 months of age

3. Growth
 - a. Weight for age Z-score (in subjects without ascites)
 - b. Height for age Z score
4. Serum biomarkers of sufficiency of fat-soluble vitamins
 - a. Vitamin A: molar ratio of serum retinol/retinol binding protein
 - b. Vitamin D: serum level of 25-hydroxy vitamin D
 - c. Vitamin E: ratio of serum vitamin E/total lipids
 - d. Vitamin K: International Normalized Ratio (INR)
5. Presence of ascites
- Tertiary outcome measures:

All measurements will be made at 12 and 24 months of age:

 1. International Normalized Ratio (INR)
 2. Serum albumin concentration
 3. Pediatric End-Stage Liver Disease (PELD) score
 4. Platelet count
 5. Serum sodium concentration
 6. Serum bile acid concentrations
 7. Serum concentration of undercarboxylated prothrombin (PIVKA-II)
 8. Head circumference Z-score
 9. Mid-arm circumference and triceps skinfold thickness
 10. Health-related quality of life (HRQOL)
 11. Neurodevelopmental assessment (Bayley score)
 12. Immunologic response to routine childhood vaccination (at 18 months of age)

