In the unlikely event that the subject develops a hypersensitivity reaction to TMP/SMZ, the medication will be discontinued promptly and oral neomycin (25/mg/kg twice a day orally) will be used for prophylaxis against ascending cholangitis. Because neomycin provides no prophylaxis against PCP, the subject will also undergo a blinded taper and discontinuation of the study drug/placebo as outlined in Section 4.F3. Our choice to discontinue the study drug/placebo is based on our concerns that the subjects would be

exposed to additional risks that would derive from adding another antimicrobial for PCP prophylaxis.

4.M7. Ranitidine

- Ranitidine (Zantac®): 12.5 mg orally twice daily (2-6 mg/kg/day) during administration of study drug/placebo
- If Zantac tablets are not available due to supply shortage from the manufacturer, Zantac liquid can be dispensed.

Because of the association between corticosteroid use and gastritis/peptic ulcer, all study subjects will receive 12.5 mg orally twice daily (2-6 mg/kg/day) throughout the duration of the administration of study drug/placebo. Monthly supplies of Ranitidine will be dispensed by the research pharmacist to the study subject's parent/guardian.

4.M8. Routine Childhood Immunizations

It is expected that routine primary immunizations will be given to all children by their primary care provider as recommended by the Committee on Infectious Diseases of the American Academy of Pediatrics (AAP), except that immunizations will not be given for the first 4 weeks after portoenterostomy (a period of time when the corticosteroid dose is 2-4 mg/kg/day). The normal immunization schedule will then be resumed, with immunizations to be given prior to one year of age being delayed by up to 4 weeks. If there is a need to catch-up with routine immunization schedule, it is anticipated that the catch-up schedule recommended by the Committee on Infectious Diseases of the AAP will be used by the primary care provider. Additional vaccines that are recommended for children with chronic liver disease are Hepatitis A and annual influenza vaccine, and will be administered as recommended by AAP guidelines.

4.M9. Steroid Pulses

The use of a steroid pulse (4-5 days of IV steroids at any time following the portoenterostomy) during this trial will be treated as a protocol violation.

4.N. Corticosteroid Treatment and Absorption of Fat-Soluble Vitamins

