Impaired neurodevelopmental outcome has also been reported in association with the use of corticosteroids in clinical trials of premature neonates with lung disease (discussed in Section 2.D3). In regard to infants with biliary atresia randomized to receive corticosteroid, it is possible that an improved liver function in these infants may improve long-term outcome and health-related quality of life, which may actually result in improved neurodevelopment. Therefore, to carefully monitor the long-term neurodevelopmental outcome, we will assess development by the Bayley Test for all subjects at 1 and 2 years of age. Testing will be performed by an appropriately trained child psychologist at each ChiLDREN clinical site. Since the effect of cholestasis and ongoing liver disease on neurodevelopment during the first two years of life has not been well characterized, data from this study will be used to determine both the effects of chronic liver disease and corticosteroid treatment on neurodevelopment. Since subjects participating in this clinical trial will also participate in the ChiLDREN prospective database study, they will also undergo neurodevelopmental testing yearly from 3-6 years, then at 8 and 10 years of age. This testing will enable additional scrutiny of potential long-term adverse effects in subjects receiving corticosteroids.

4.O3. Compromised Immune Function

Subjects with biliary atresia have increased incidence of ascending cholangitis, bacteremia, and spontaneous bacterial peritonitis. The immunologic response to routine childhood immunizations may also be variable, with failure to reach adequate antibody geometric mean titers to vaccine agents in some subjects⁷⁴⁻⁷⁶. Recognizing that treatment with corticosteroids also places infants at risk of compromised immune function, we will monitor all subjects participating in this study for clinically significant immunologic dysfunction (Table 8).

Table 8. Summary of Monitoring Strategy to Detect Potential Compromise in Immune Function.

Impaired responses to childhood vaccines	Assess antibody titers to vaccine antigens at 18 months of age. Recommend to the primary health care provider to administer booster vaccine if serum titer is less than the minimal protective titer. No live viral vaccines should be administered until 3 months after completion of study drug/placebo

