Development of infectious diseases and vaccine-preventable diseases	All emergency department visits and hospitalizations will be reported as an adverse event. If the subject is hospitalized with lower respiratory tract symptoms of unknown etiology, nasal wash will be obtained for pertussis PCR. If S. pneumoniae is isolated from the blood or a sterile body site (such as cerebrospinal fluid), isolates will be serotyped.
Development of septicemia and opportunistic infections	All events with bacteremia, fungemia, or other opportunistic infections will be reported as an adverse event.

Impaired response to childhood vaccines

Subjects will receive all routine childhood vaccines according to the schedule recommended by the American Academy of Pediatrics (AAP), with the exception of up to a 4-week delay of vaccines that would have been given during the first 4 weeks of the study drug/placebo. Vaccinations will be administered by the subject's primary care provider. At 18 months of age or at the time of liver transplantation (if younger than 18 months of age), the vaccination records of each subject will be obtained from the primary care provider for review. The number and size of doses, dates of administration, and vaccine manufacturer will be recorded. At the age of 18 months, 6-9 ml of blood will be obtained to measure serum antibody titers against individual vaccine antigens. The antibody titers will be measured by the study sites local laboratory. If a subject has received a transplant before the 18th month visit, titers should not be collected. Priority titers to be collected relate to vaccinations for Hepatitis B, Tetanus, and Polio. If serum antibody titers do not achieve protective levels as determined by the local laboratory standard and the investigator, the information will be provided to the primary care provider so that booster/re-immunization of appropriate antigen(s) is given. Absent titers will also be communicated to the primary care provider, who will treat with re-immunization as directed by the AAP guidelines for catch-up immunization.

Development of infectious diseases and vaccine-preventable diseases

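### Sections 4.M8 and 4.O3 let all routine vaccines resume after about 4 weeks, while Table 8 bars live viral vaccines until 3 months after study drug/placebo ends, and nothing links the two rules

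*Protocol*

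**What the plan says.** Three places in the current protocol govern vaccination after enrolment.

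- **Section 4.M8 (Routine Childhood Immunizations)** says that "immunizations will not be given for the first 4 weeks after portoenterostomy", and explains that the steroid dose is 2-4 mg/kg/day in that period. It continues: "The normal immunization schedule will then be resumed, with immunizations to be given prior to one year of age being delayed by up to 4" (the unit being weeks). Any catch-up is expected to follow the American Academy of Pediatrics (AAP) schedule. Live vaccines are not mentioned.
- **Section 4.O3, prose on impaired vaccine response**, has subjects receive every routine childhood vaccine on the AAP schedule, "with the exception of up to a 4-week delay of vaccines that would have been given during the first 4 weeks of the study drug/placebo". No other exception is stated. The primary care provider gives the vaccines.
- **Section 4.O3, Table 8**, in the row on the same topic, says: "No live viral vaccines should be administered until 3 months after completion of study drug/placebo".

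Two other places bear on live vaccines. Section 4.D excludes "Infants who have received the live attenuated rotavirus vaccine (e.g. Rotateq) within 5 days prior to proposed administration of study drug", and 4.F1 delays the first steroid dose in infants vaccinated earlier than that until 5 days have passed. Both concern doses given before study drug. The Amendment 4 rationale for those additions cites the manufacturer's contraindications and concludes that no child would receive rotavirus vaccine once biliary atresia is diagnosed.

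**The concern.** The protocol names compromised immune function as a risk of the treatment and puts a restriction on live viral vaccines in Table 8. The section a site would open for vaccination instructions, 4.M8, does not carry that restriction. Nor does the prose directly below Table 8, which words the short delay as the sole exception.

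By tying its 4-week hold to the 2-4 mg/kg/day dose, 4.M8 also invites the reader to conclude that vaccination in general is acceptable once the dose drops in week 5. A site working from 4.M8 or the 4.O3 prose could therefore, without noticing, allow something Table 8 forbids while the infant is still on study drug/placebo. Because vaccines are given by the primary care provider, what happens depends on which passage the site passes on.

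**Working it through.** The protocol states no figure of its own for this point. The check sets the passages side by side and applies date arithmetic.

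**Inputs**
- Start of study drug: within 72 hours of surgery, so day 0 to 3 (4.F1).
- Duration: 4.A says "Randomize the subject to 13 weeks of treatment with placebo or corticosteroids", that is 13 × 7 = 91 days.
- End of the 4.M8 hold: 4 × 7 = day 28 after surgery.
- End of the Table 8 restriction: last day of study drug plus 3 months, taken as 3 × 30.44 ≈ 91.3 days.

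**Dates for an infant who completes treatment**
- Study drug ends on day 0 + 91 = 91 to day 3 + 91 = 94 (week 13.0 to 13.4).
- The Table 8 restriction ends on about day 91 + 91.3 = 182 to day 94 + 91.3 = 185 (week 26.0 to 26.5).
- The passages differ for (182.3 − 28)/7 = 22.0 to (185.3 − 28)/7 = 22.5 weeks.
- Of that, (91 − 28)/7 = 9.0 to (94 − 28)/7 = 9.4 weeks are on study drug/placebo. In the active arm, Table 4 gives 1 mg/kg/day in weeks 5-6, falling to 0.1 mg/kg every other day in weeks 12-13.

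**In terms of age**, over an assumed range of age at surgery (the parent database enrols infants up to 180 days old, section 3.A):

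| Age at surgery (days) | 4.M8 resumes (months of age) | Table 8 lifts (months of age) |
|---|---|---|
| 30 | 1.9 | about 7 |
| 60 | 2.9 | about 8 |
| 90 | 3.9 | about 9 |
| 120 | 4.9 | about 10 |
| 180 | 6.8 | about 12 |

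If surgery is at or before about 180 days of age, the point concerns live viral vaccines due before about 12 months of age.

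**Side by side**
- *Scope:* 4.M8 and the 4.O3 prose cover routine vaccines as a whole; Table 8 covers live viral vaccines only.
- *Clock:* 4.M8 counts from surgery, the 4.O3 prose from the start of study drug, and Table 8 from its completion. If study drug stops early under Table 5, and completion is read as the last dose taken, the Table 8 date moves earlier and the window shortens.
- *Linkage:* neither 4.M8 nor the 4.O3 prose refers to the Table 8 restriction, and Table 8 does not say that it overrides them.

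**The case against.** The strongest reply is that these are a general rule and a specific one. A site can satisfy both by resuming the schedule in week 5 and withholding live viral vaccines, and Table 8 sits directly above the prose it is said to contradict. That is a natural reading, but the document does not state it, and the 4.O3 wording leaves no room for a second exception.

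Several further objections stand and limit the point:

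- 4.M8 defers to AAP recommendations. Their content is not in the protocol, and they may already restrict live vaccines during steroid treatment. It cannot be said that 4.M8 positively authorises one.
- Rotavirus is the only vaccine the protocol identifies as live, and the Amendment 4 rationale says it would not be given after diagnosis. Reading 4.D and 4.F1 as evidence of rotavirus exposure after enrolment would ignore that statement. What remains is that 4.M8 and 4.O3 do not carry it.
- A reader might infer a conflict lasting 22 weeks in each of the 140 infants. The documents do not support this: 22 weeks is the gap between two dates, and it has consequences only where a live viral vaccine falls due inside it.
- A reader might also infer that the 18-month titers are distorted. This is not shown. Vaccine response is a tertiary, hypothesis-generating outcome; the priority titers are hepatitis B, tetanus and polio, none of which the protocol labels as live; and doses and dates of vaccination are recorded.
- A reader might assume the primary care provider is blinded. Section 4.A says so only of the research team.

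**Conclusion.** The contradiction is in the current text and holds as written. Section 4.M8 and the 4.O3 prose permit all routine vaccines after a hold or delay of up to 4 weeks; Table 8 bars one class of them until about week 26 after surgery. For an infant completing 13 weeks of treatment the gap is about 22 weeks, about 9 of them on study drug/placebo.

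This rests on full treatment duration, a start within 72 hours of surgery, and 3 months taken as about 13 weeks. The number of infants who would actually meet the conflict cannot be derived from the protocol and may be small. The matter is one of participant safety and internal consistency. It does not touch the primary analysis.

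**What to change.** Reconcile 4.M8, the 4.O3 prose and Table 8 into one rule chosen by the sponsor. The rule should:

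- say how live viral vaccines are handled relative to study drug/placebo, including which clock applies;
- appear in the same words, or by cross-reference, in all three places;
- be consistent with the Amendment 4 statement on rotavirus vaccine after diagnosis;
- be the rule that sites give to primary care providers.

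This review does not say which interval is right. The cost is a wording amendment and consistent text for communication with primary care providers. No visit, test, sample-size or analysis change is needed.

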Two central laboratories will be measuring vitamin levels for this study. A sample will be sent to the Pediatric CTSC Core Laboratory at The Children's Hospital in Denver which will perform all the tests except the PIVKA-II. The samples that are sent to Denver will be identified with the following personal health information: child's name, medical record number, and date of birth. The child's unique study code will not be shared. It is necessary for this information to be collected and shared because these are clinically indicated tests that will be reported to the site. These tests will be paid by the study.

PIVKA-II samples will be barcoded and sent to the NIDDK Repository . The NIDDK Repository will then batch ship these samples to Cincinnati Children's Hospital Medical Center for processing. The NIDDK Repository will verify which samples were sent to Cincinnati, and Cincinnati will send the results to the DCC. PIVKA-II is not being used clinically by the sites and these results will not be reported back to the site. These tests will be paid by the study.

Target vitamin levels:

- Vitamin A: A molar ratio of retinol:RBP will be used to assess vitamin A nutriture. A cut-off of 0.8 mol/mol will be used to define vitamin A deficiency. If a retinol:RBP ratio is below 0.8 and serum retinol is less than 20 ug/dl, the subject will be considered vitamin A deficient and supplementation will be recommended (see below). If the serum retinol is <20 ug/dl and the retinol:RBP ratio is >0.8, vitamin A status will be reassessed in one month. If the serum retinol is > 20 ug/dl and the ratio is < 0.8, vitamin A status will be reassessed in one month. If the serum retinol is greater than the upper limit of normal range, the vitamin A dose will be decreased by 50% and vitamin A status reassessed in one month.
- Vitamin D: The target serum 25-OH vitamin D concentration range is 15-45 ng/ml.
- Vitamin E: The target serum vitamin E:lipid ratio will be >0.6 mg/g in children less than 12 months of age and >0.8 mg/g in children older than 12 months of age. The upper limit of vitamin E:total lipids ratio will be 3.5 mg/g.
- Vitamin K: The INR will be used as surrogate marker of vitamin K status with a target INR<1.2

Target vitamin concentration within normal range: When vitamin concentrations are within target range no changes will be made and vitamin levels will be retested at the 3 and 6 month follow-up visit and at 12, 18 and 24 months of age while a subject is receiving vitamin supplementation.

Target vitamin concentrations below normal range: When a vitamin result is below target range, supplementation of the specific vitamin(s) that is deficient will be prescribed and re-checked in one month (see Section 4.N9 for supplementation plan). If the vitamin level is within the target range there will be no further adjustments. When the vitamin level is still below target range, additional supplementation will be given as outlined below (Section 4.N9).

Target vitamin concentrations above normal range: When a subject is receiving the standard vitamin supplementation and one or more vitamin concentrations is above target range, the vitamin supplementation may be reduced to 1 ml per day and the vitamins that were within target range will be supplemented individually to have the same concentration as in the formulation of 2 ml of AquADEK®. All vitamins will be rechecked within one month and adjustments made as outlined in the protocol.

4.N10. Adjustment of Individual Vitamin Doses

When individual vitamins are found to be deficient, the vitamin will be prescribed, whenever possible, at the amount described below:

- Vitamin A: When a subject is vitamin A deficient, liquid vitamin A (intravenous preparation) may be given at 5000 IU by mouth with the AquADEK® each day and vitamin A status rechecked within one month. Doses orally of up to 25,000 – 50,000 IU vitamin A per day can be given for 1-4 weeks but will require weekly monitoring of vitamin status to prevent toxicity. Alternatively, when a subject is vitamin A deficient, 50,000 IU IM may be given once a month for two months. Vitamin A status is rechecked monthly with this regimen.

- Vitamin D: If a subject is vitamin D deficient, cholecalciferol or ergocalciferol will be given at 1200-4000 IU by mouth with the liquid formulation each day. Vitamin D status will be reassessed in one month. If the subject remains vitamin D deficient, the oral dose will be increased to 4000-8000 IU by mouth to be given each day. Alternatively, 1,25 OH₂ D may be prescribed at a dose of 0.05 – 0.2 µg/kg/day. Vitamin D status will be reassessed in one month. If 1,25 OH₂D is administered, then serum 1,25 OH₂D levels need to be monitored by the clinical site physician. If the serum concentration of the appropriate vitamin D metabolite is still deficient, the vitamin D dose will be increased to 12,000 IU by mouth and vitamin D status reassessed in one month. If the 25 OH-vitamin D level still remains below normal, the clinical site physician will decide to prescribe either 1,25 OH₂ vitamin D supplementation or give intramuscular vitamin D and monitor as necessary. If 25-OH vitamin D blood levels exceed 60 ng/ml, then serum calcium and phosphate should be checked, and the vitamin D dose should be reduced by 50% and levels repeated in 2 to 4 weeks.
- Vitamin E: If a subject is vitamin E deficient, additional TPGS will be prescribed at 25 IU/kg/day and vitamin E status will be reassessed in one month. If the subject remains deficient, 50 IU/kg/day of TPGS will be prescribed and the vitamin E status will be reassessed in one month. Rarely will a subject not respond to this dose of TPGS. However, if unresponsive, TPGS dose can be increased up to 100 IU/kg/day given in 2 or 3 divided doses to prevent diarrhea, with monitoring of vitamin E status in 1 month.
- Vitamin K: If a subject is vitamin K deficient with an INR > 1.2 but ≤1.5, 2.5 mg of vitamin K by mouth every day will be prescribed. The PT/INR will be rechecked within 7-10 days. If the INR is rechecked and it is not less than target ratio of <1.2, 5 mg vitamin K by mouth every day will be prescribed. The PT/INR will be rechecked within 7 days-10 days.

If the INR is > 1.5 and ≤1.8, 5 mg vitamin K by mouth every day will be prescribed and/or 2-5 mg vitamin K may be administered intramuscularly and the PT/INR will be rechecked within 7-10 days. If there is any clinically significant bleeding the use of parenteral vitamin K and FFP will be decided by the site PI according to local standard of care.

When the INR is > 1.8, 2-5 mg vitamin K may be administered intramuscularly and/or 5 mg of vitamin K by mouth daily may be prescribed at the discretion of the clinical site physician. If there is any clinically significant bleeding, the use of parenteral vitamin K and FFP will be decided by the site PI according to local standard of care. The PT/INR will be rechecked within 7-10 days and again 1 month later. Additional doses of parenteral vitamin K will be given at the discretion of the clinical site physician, as clinically indicated.

When the subject is vitamin K deficient with any abnormal INR listed above, a repeat PT/INR is obtained 7-10 days after vitamin K supplementation. PIVKA-II levels will be obtained at the same time as the PT/INR.

4.N11. Monitoring of Serum Levels of Bile Acids

The intraluminal concentration of bile acids plays an important role in regulating absorption of fat-soluble vitamins. In biliary atresia, the excretion of bile acids into the duodenum is significantly impaired by variable degrees of biliary flow. This is associated with a rise in serum levels of bile acids. Therefore, we will measure serum bile acids prospectively in all study subjects. Serum levels will be used in future analysis to determine their correlation with serum vitamin levels, and whether they have predictive value in vitamin nutriture status.

4.O. Potential impact of Biliary Atresia and Corticosteroids on Growth, Neurodevelopmental Outcome, and Immune Function

Progression of liver disease in infants with biliary atresia after portoenterostomy often leads to malnutrition and growth failure. These subjects may also have recurrent infections, such as ascending cholangitis, suboptimal immunologic response to routine childhood immunization, and impaired neurodevelopmental outcome. Because some of these undesirable outcomes may also be associated with prolonged corticosteroid use in children without biliary atresia, we will carefully monitor them prospectively in all infants receiving study drug or placebo. The data will be analyzed to determine whether corticosteroid treatment improves (decreases) or exacerbates (increases) their incidence when compared to placebo-treated infants.

4.O1. Growth

Anthropometric measurements will be obtained at the time of hospital discharge and at follow-up visits (Table 6) throughout the duration of the study. Body weight will be determined with an electronic scale accurate to 0.1 kg. Length and head circumference will be obtained in triplicate using a measuring tape and reported in centimeters. The average of three results will be used for analysis. Weight, length, and head circumference will be compared with the CDC 2000 growth charts⁷³, and Z-scores will be derived.

Short-term impairment in linear growth may occur in subjects randomized to receive corticosteroid treatment; however, long-term growth impairment is not anticipated. It is also possible that infants treated with corticosteroids will have better liver function and actually improve growth. Given the degree of variability in growth in each infant with biliary atresia in the control group (infants without corticosteroid treatment), it is not possible a priori to define a threshold for an adverse event related to growth failure.

4.O2. Neurodevelopmental Outcome

There are no prospective, case-controlled studies assessing long-term neurodevelopmental outcome in children with biliary atresia. Suboptimal neurodevelopment, however, may result as a consequence of the chronic, debilitating disease that results from progressive liver dysfunction and recurrent hospitalizations.

Impaired neurodevelopmental outcome has also been reported in association with the use of corticosteroids in clinical trials of premature neonates with lung disease (discussed in Section 2.D3). In regard to infants with biliary atresia randomized to receive corticosteroid, it is possible that an improved liver function in these infants may improve long-term outcome and health-related quality of life, which may actually result in improved neurodevelopment. Therefore, to carefully monitor the long-term neurodevelopmental outcome, we will assess development by the Bayley Test for all subjects at 1 and 2 years of age. Testing will be performed by an appropriately trained child psychologist at each ChiLDREN clinical site. Since the effect of cholestasis and ongoing liver disease on neurodevelopment during the first two years of life has not been well characterized, data from this study will be used to determine both the effects of chronic liver disease and corticosteroid treatment on neurodevelopment. Since subjects participating in this clinical trial will also participate in the ChiLDREN prospective database study, they will also undergo neurodevelopmental testing yearly from 3-6 years, then at 8 and 10 years of age. This testing will enable additional scrutiny of potential long-term adverse effects in subjects receiving corticosteroids.

4.O3. Compromised Immune Function

Subjects with biliary atresia have increased incidence of ascending cholangitis, bacteremia, and spontaneous bacterial peritonitis. The immunologic response to routine childhood immunizations may also be variable, with failure to reach adequate antibody geometric mean titers to vaccine agents in some subjects⁷⁴⁻⁷⁶. Recognizing that treatment with corticosteroids also places infants at risk of compromised immune function, we will monitor all subjects participating in this study for clinically significant immunologic dysfunction (Table 8).

Table 8. Summary of Monitoring Strategy to Detect Potential Compromise in Immune Function.

Impaired responses to childhood vaccines	Assess antibody titers to vaccine antigens at 18 months of age. Recommend to the primary health care provider to administer booster vaccine if serum titer is less than the minimal protective titer. No live viral vaccines should be administered until 3 months after completion of study drug/placebo
Development of infectious diseases and vaccine-preventable diseases	All emergency department visits and hospitalizations will be reported as an adverse event. If the subject is hospitalized with lower respiratory tract symptoms of unknown etiology, nasal wash will be obtained for pertussis PCR. If S. pneumoniae is isolated from the blood or a sterile body site (such as cerebrospinal fluid), isolates will be serotyped.
Development of septicemia and opportunistic infections	All events with bacteremia, fungemia, or other opportunistic infections will be reported as an adverse event.

Impaired response to childhood vaccines

Subjects will receive all routine childhood vaccines according to the schedule recommended by the American Academy of Pediatrics (AAP), with the exception of up to a 4-week delay of vaccines that would have been given during the first 4 weeks of the study drug/placebo. Vaccinations will be administered by the subject's primary care provider. At 18 months of age or at the time of liver transplantation (if younger than 18 months of age), the vaccination records of each subject will be obtained from the primary care provider for review. The number and size of doses, dates of administration, and vaccine manufacturer will be recorded. At the age of 18 months, 6-9 ml of blood will be obtained to measure serum antibody titers against individual vaccine antigens. The antibody titers will be measured by the study sites local laboratory. If a subject has received a transplant before the 18th month visit, titers should not be collected. Priority titers to be collected relate to vaccinations for Hepatitis B, Tetanus, and Polio. If serum antibody titers do not achieve protective levels as determined by the local laboratory standard and the investigator, the information will be provided to the primary care provider so that booster/re-immunization of appropriate antigen(s) is given. Absent titers will also be communicated to the primary care provider, who will treat with re-immunization as directed by the AAP guidelines for catch-up immunization.

Development of infectious diseases and vaccine-preventable diseases

Subjects will be prospectively monitored for the development of infectious diseases and vaccine-preventable diseases. Treatment with corticosteroids often induces a leukocytosis (with or without mild bandemia). This leukocytosis is usually benign and expected to decrease as the dose of corticosteroid decreases. If leukocytosis is associated with any other signs or symptoms that may indicate infection (e.g.: fever, lethargy, poor feeding), the primary care provider will further evaluate and treat as clinically indicated, according to local standard of care.

Parents and primary care providers of all enrolled subjects will be instructed to contact the study coordinator promptly at the time of any infectious acute illness that leads to visit to the primary care provider, to an emergency department, or if the subject requires hospitalization. An Adverse Event Form will be completed within 24 hrs of each report. If a child is hospitalized because of a respiratory tract illness of unknown etiology, microbiology studies will be pursued according to the local standard of care, but an additional nasal aspirate will be obtained for rapid screen for *B. pertussis*. If *S. pneumoniae* is isolated from a sterile body site (e.g.: blood, cerebrospinal fluid) or lower respiratory tract by bronchial lavage, the isolate will be serotyped to determine if it is a vaccine-related strain. These diagnostic studies will be performed, when possible, by the admitting hospital's clinical microbiology laboratory; alternatively, samples may be performed by an outside laboratory, such as Quest Diagnostic Laboratories.

Development of septicemia and opportunistic infections

Subjects will be monitored for the development of infections or serious opportunistic infections (bacterial, viral, fungal). Evaluation of the subject with a febrile illness will proceed as per the local standard of care and antimicrobials will be initiated accordingly. completed. If the infection is associated with hypotension, acidosis, or tissue necrosis, a Serious Adverse Event Form will be completed. The decision to break the study medication code and institute stress dose replacement with corticosteroid for subjects in the corticosteroid arm of the study will be made by the clinical center PI based on the clinical status of the subject. If a serious opportunistic infection is diagnosed, appropriate antimicrobial therapy will be initiated and a Serious Adverse Event Form will be completed. If the subject is still receiving study drug/placebo, the drug/placebo will be tapered and discontinued according to the protocol outlined in Table 5.

4.P. Research Versus Standard Clinical Care

One important feature of this clinical trial is that subjects will receive standard clinical care at ChiLDREN centers in addition to the care related to enrollment in the trial. As outlined in Table 9, participation in this trial will specifically require: 1) randomization to receive either corticosteroids or placebo, 2) treatment with ranitidine during the duration of study drug/placebo, 3) outpatient visit at 2 weeks after portoenterostomy, 4) serum concentration of electrolytes, glucose, bile acids, and PIVKA-II, 5) developmental assessment, 6) HRQOL inventory, and 7) evaluation of serum antibody titers to vaccines. All other outpatient visits and laboratory studies are routinely performed as part of standard clinical care of infants with biliary atresia, as summarized in Table 9 below.

Table 9. Outline of Care Related to this Clinical Trial Versus Standard Clinical Care

Health Care Item	Collected by*
Medical encounters/visits	
• 2 weeks after portoenterostomy	T
• 1,2,3,6 months after portoenterostomy	DB,CC
• 12,18,24 months after portoenterostomy	DB,CC
Standard diet and nutritional support	DB,CC
Vitamin supplementation	T
Ursodeoxycholic acid	T
Antibiotic prophylaxis for ascending cholangitis	DB,CC
Administration of study drug/placebo	T
Administration of ranitidine	T
Childhood immunizations	CC
Laboratory monitoring	
• Complete blood count	DB,CC
• LFTs, PT/INR	DB,CC
• Serum retinol, RBP, 25OH-Vitamin D	CC,T
• Serum vitamin E, total lipid ratio	CC,T
• Serum bile acids, PIVKA-II	T
• Serum electrolytes, glucose	T
• Antibody titer against routine immunizations	T
Neurodevelopmental assessment	DB
HRQOL	DB

* T=Collected by this clinical Trial;
 DB=Collected as part of ChiLDREN prospective Data Base; informed consent obtained to share the information with the clinical trial.
 CC=Collected as part of standard Clinical Care.

